Prospective, single-centre, cohort study assessing the potential application of WOUNDCHEK™ diagnostics for ulcer management

(BIOME, Bacterial Infection: Observation & Management Evaluation)

V1, dd 18 November 2022

Chief Investigator's Statement of Ownership and Content.
I, [name], confirm that this protocol is my work and is owned by me. The protocol conforms to standards outlined in the Declaration of Helsinki 1964.
Name (PRINT):
Signature:
Date:

RESEARCH PROTOCOL SUMMARY

TITLE:	Prospective, single-centre, cohort study assessing the potential application of WOUNDCHEK™ diagnostics for ulcer management
Short title:	BIOME, Bacterial Infection: Observation & Management
	Evaluation
IRAS number	314595
Device description	CE-marked point of care test: WOUNDCHEK™.
	WOUNDCHEK™ Bacterial Status — or WCBS - is able to detect bacterial EPA (elevated protease activity). WOUNDCHEK™ Bacterial Status will help clinicians establish within minutes which wounds may most benefit from a protease modulating therapy, ensuring appropriate and targeted use of these therapies.
Study design	Prospective, single-centre, controlled, non-randomised, prospective cohort comparative study
	Participants' index ulcer will be swabbed twice, at week 0 and at week 6, plus a medium-term assessment at week 12.
Primary objective	Determine if there is a difference in rate of positive outcome between clinical opinion (ie presence of infection based on wound symptoms) and WOUNDCHEK™ Bacterial Status test result for the same wound.
Secondary objectives	To define the degree of concordance between a clinical staff member's opinion and results from the WOUNDCHEK™ detection kit, concerning the assessment of infection presence in ulcer wounds.
	Determine what patient and/or wound characteristic(s) are significantly linked to a non-matching result between clinical opinion and WOUNDCHEK™ WCBS result. These outcomes are relevant for application of the WOUNDCHEK™ test in standard clinical practice. Two binary logistic regression analyses will be conducted for variables associated with the sample's proportion of non-matched outcome: - Clinical opinion negative ('no infection') vs WOUNDCHEK™ test positive or - Clinical opinion positive ('possible' or 'definite' infection) vs WOUNDCHEK™ test negative
	Evaluate if there are factors associated with infection rates and/or WOUNDCHEK™ result, including clinical indicators of infection such as erythema, purulence, odour, and patient characteristics (health status, co-morbidities, demographic).
	Assess if there are any trends in bacterial protease detection rates in ulcers when patients are followed up, ie result of first test versus second follow-up test of same ulcer
	Evaluate if clinical staff deviate from their initial treatment plan once the WOUNDCHEK result is available to them during a consultation

	T
Inclusion & Exclusion	Inclusion criteria:
criteria	- Adult patients aged ≥ 18 years
	- Patients can be newly presenting to or existing users of the
	specialist service in question (eg podiatry, vascular surgery)
	- Patients with recurrent wounds, including multiple wounds, are
	eligible; largest ulcer to be index wound - If infection occurs and antibiotics applied, whilst in study, then
	this is not deemed an exclusion criterion.
	 Prophylactic systemic antibiotic use is not an exclusion criterion
	- Chronicity: clinical diagnosis of ulcer with wound duration > 30
	days.
	- Wound type:
	 Leg ulcer (can be venous, mixed or arterial in nature)
	 Foot ulcer (can be diabetic or non-diabetic in nature)
	Exclusion criteria:
	- Aged < 18 years
	- Any reasons for the patient being unable to follow the protocol,
	including lack of mental capacity to consent to taking part in the
	study.
	- The patient has concurrent (medical) conditions that in the
	opinion of the investigator may compromise patient safety or
	study objectives
	- Confirmed and ongoing wound infection at baseline which is
	already being treated with systemic antibiotics (within 3 weeks
	of first study visit) Previous participation in BIOME study
	- Trevious participation in biolivic study
Sample size	258 samples required, taken from minimum of 129 patients at week0
	and week6 visits. This study element is powered to detect a 4%
	difference in detection of clinician-specified wound infection and a
	positive WOUNDCHEK™ Bacterial Status test result. (Chi-squared test,
	80% power, p-value 0.05, 10% attrition rate). This is provided the
	incidence of infection detected equals 9% and 5% per rater,
	respectively.
	Furthermore, the study is also sufficiently powered to detect an inter-
	rater concordance level (Kappa) of 0.9, at 80% power and an infection detection rate of 10%.
	detection rate of 10%.
Manufacturer & provider	WOUNDCHEK™ Laboratories

Chronic ulcer wounds of the legs and feet can be challenging for healthcare staff to manage. Patients often have co-morbidities and there is a considerable likelihood of non-healing and recurrence of ulcers, plus infection can occur. Apart from having a significant negative impact on patients' lives, it is also a huge economic burden to the National Health Service. Clinical opinion — by checking for hallmark signs of infection - is the main way to determine if a wound is infected. Microbiology testing offers information on what type of antibiotic may help to treat the infection. Different companies have developed point-of-care tests that assess something that cannot be readily observed: bacterial protease activity. Its presence may be indicative of infection since bacteria use said protease enzymes to break down protein structures in a wound that are needed for a wound to heal. Due to logistic and cost reasons it would not be practical to apply a protease point-of-care test for all patients' wounds. This study investigates to what degree clinical opinion and results of the WOUNDCHEK Bacterial Status test align, and also what factors and variables may be associated with non-matching results. Furthermore, the degree of influence the WOUNCHEK test result may have on clinical management of chronic lower limb ulcers will be explored. For this purpose a total of 258 wounds (minimum of 129 patients) will be assessed at baseline and then six and twelve weeks later.

1 BACKGROUND AND RATIONALE

Leg and foot ulcers can occur for various reasons, see Figure 1. Though venous leg ulcers (VLUs) are the most common type of leg ulcers, contributing to the majority of leg ulcers, there are many patients who have ulcers due to a mixed venous-arterial or other underlying condition (SIGN 2010, Graham *et al* 2003). The natural history of the disease – particularly in those patients who have venous insufficiency and or other chronic disease affecting the vasculature such as diabetes and peripheral arterial disease - is a continuous cycle of healing and breakdown over decades. VLUs are associated with considerable expense, morbidity and impaired quality of life (Persoon *et al* 2004). A positive relationship has been observed between VLU occurrence and specific modern lifestyle risk factors such as sedentary lifestyles and obesity (Brand *et al* 1998). Table 1 shows annual NHS cost for treating VLUs compared to other chronic wound treatments. Similar to VLUs, the occurrence of diabetic foot ulcer (DFU) is a common complication of diabetes with enormous cost implications, totalling £650 million per year once associated morbidity is taken into account (NHS Diabetes report).

Table 1. Chronic wound treatment costs to the NHS (Posnett & Franks 2008)

	Annual incidence	Cost per patient	Annual NHS cost (2005–2006)
Venous leg ulcers	108,600	£1,500-1,800	£168–198m
Foot ulcers	57,000	£5,200	£300m
Pressure ulcers	410,000	£4,300-6,400	£1.8-2.6bn
TOTAL	575,600	£4,000-5,400	£2.3-3.1bn

Figure 1, Different causes of leg ulcers (Agale 2013)

	Venus
Vascular	Arterial
	Mixed
	Diabetes
Neuropathic	Tabes
	Syringomyelia
	Diabetes
Metabolic	Gout
	Prolidase deficiency
IIt.l	Sickle cell disease
Haematological	Cryoglobulinemia
	Pressure
Trauma	Injury
	Burns
Tumors	Basal cell carcinoma
Tulliors	Squamous cell carcinoma
	Bacterial
Infection	Fungal
	Protozoal
Panniculitis	Necrobiosis lipoidica
rannicunus	Fat necrosis
Pyoderma	Gangrenosum
Special	Hypertensive ulcer

Bacterial infection of wounds carries the risk of further degenerative complications including cellulitis, necrotising fasciitis, and sepsis (Grothier, 2015). Specific wounds, such as diabetic foot ulcers may lead to amputation if osteomyelitis develops. An additional undesirable effect of infection of wounds is that it delays – or stops altogether – the wound healing process (Halbert et al, 1992).

Detection of chronic leg/foot ulcer infection remains reliant on clinical judgement. For example, imaging modalities such as MRI do not perform better than clinical appraisal in terms of sensitivity and specificity when it comes to detecting osteomyelitis (Dinh et al, 2008). Quantitative detection of infection is still undertaken by swabbing the wound and then culturing the pathogens in a microbiology laboratory. Obtaining these results generally takes days; even molecular profiling does not give an instant result. Microbiological counts and species identification do not necessarily reflect infection as defined by other assessments, as demonstrated by Gardner et al (2014).

Clinical guidelines stipulate that the only available laboratory-based diagnostic option, microbiological testing, should only be used to identify the pathogen strain in clinically confirmed infection. Therefore, clinical opinion is the mainstay of predicting and diagnosing infection (NICE, 2008, 2015). The lack of a simple cost-effective and repeatable testing method may have three consequences: 1) lack of uniformity in diagnosis, due to differences in clinical judgement, which in turn may result in 2) over-diagnosis of infection with inappropriate prescription of antibiotics or antimicrobial dressings, or 3) late presentation of patients with systemic signs and spreading cellulitis or osteomyelitis requiring hospital admission and treatment with intravenous antibiotics or emergency surgery.

O'meara and colleagues (2006) concluded from a systematic review on clinical examination, sample acquisition and sample analysis in DFUs that there is a lack of evidence regarding what samples should be taken and how they should be analysed. They did suggest that semi-quantitative sample analysis – a category that the WOUNDCHEKTM protease detection kit (called WOUNDCHEKTM) would fall under – may be a useful alternative to quantitative analysis. The provision of a rapid, reliable, sensitive and relatively low cost infection detection test kit for bacterial protease presence (which can be highly indicative of infection), which can be used at point-of-care, has the potential to provide the NHS with significant cost savings as well as improving the outcomes for patients.

Outcome data from another study which appraised the Glycologic bacterial protease detection kit showed an agreement in terms of wound assessment for 'infection' – between podiatrists' clinical opinion and Glycologic test result - in 79% of samples (301 out of 383 wound assessments), where podiatrists identified more (possible) infections than the Glycologic kit (55 [15%] vs 14 [4%] swabs respectively). Regression analysis and primary component analysis shows that clinical signs of wound infection, namely erythema, purulence and odour, are all significantly associated with both a positive clinical opinion and Glycologic test result (Jonker et al 2022a, Jonker et al, 2022b). The same study also corroborated earlier research that bacterial load of a wound is not indicative of bacterial protease activity and clinical opinion of infection. Initial research involving the WOUNDCHEK™ Bacterial Status test also suggests that the degree of bacterial load does not correlate with the degree of pathogenesis exhibited by said bacteria (Serena et al, 2022; Benson et al 2017). On the other hand, unlike with Glycologic, the WOUNDCHEK™ Bacterial Status test did not find a strong association between clinical signs of infection and a positive WCBS test. This study did, however, not report on individual hallmark signs of infection such as erythema, purulence and odour (Serena et al 2022).

2 OBJECTIVES

2.1 PRIMARY OBJECTIVE

Determine what patient and/or wound characteristic(s) are significantly linked to a non-matching result between clinical opinion and WOUNDCHEK™ Bacterial Status (WCBS) result. These outcomes will be relevant for application of WOUNDCHEK™ test in standard clinical practice. See Table 2.

Table 2. Outcome options for WOUNDCHEK $^{\text{\tiny M}}$ and clinical inspection, with the two non-matching outcome options shaded in green and blue respectively.

	WOUNDCHEK™	WOUNDCHEK™
	Bacterial Status	Bacterial Status
Clinical opinion:	negative	Positive
no infection		
Clinical opinion:	negative	Positive
possible infection		
Clinical opinion:	negative	Positive
infection		

2.2 SECONDARY OBJECTIVES

The level of concordance between a clinical staff member's opinion and results from the WOUNDCHEK™ detection kit defining the assessment of infection presence in lower limb ulcers.

Evaluate if there are factors associated with infection rates and/or WOUNDCHEK™ result, including clinical indicators of infection such as erythema, purulence, odour, and patient characteristics (health status, co-morbidities, demographic). These include, but are not restricted to:

- Type of wound
- Wound size
- Chronicity of wound
- Clinical indicators of infection, including degree of erythema, purulence, and pain
- Presence of co-morbidities
- Patient health status
- Clinical rater

Assess if there are any trends in bacterial protease detection rates in ulcers when patients are followed up, ie result of first test versus second follow-up test of same ulcer

Evaluate if clinical staff deviate from their initial treatment plan once the WOUNDCHEK result is available to them during a consultation.

3 INVESTIGATIONAL PLAN

3.1 TRIAL DESIGN AND TIMELINE

The study is a prospective, single-centre, non-randomised, observational design. There is no 'gold standard' accepted detection test for infection available. Clinical guidelines stipulate that clinical judgement concerning the presence or absence of infection is the recommended clinical practice. Samples should only be sent off to a microbiology department to confirm the causative pathogen and inform choice of antibiotics. Therefore, the results of the novel detection infection test kit will be compared with the clinical staff member's judgement of infection status. Table 2 shows the anticipated timeline for the study. Appendix 3 summarises the patient pathway for the study.

For this study, appropriate clinical staff (vascular nurses, practice nurses, tissue viability or podiatry staff) will provide judgements on leg/foot wound infection status. This (ultimately subjective) evaluation can potentially contribute to variability in the detection of infection.

During the study period, all patients can continue to be managed and receive their standard treatment regime by their usual clinical team. Wound dressing selection, dressing frequency and all other aspects of their wound care will continue to be the responsibility of the clinical team. This study will, however, record if the clinical staff member was influenced by the WOUNDCHEK result in terms of dressing choice, antibiotics use, microbiological test swabbing, and interaction with the multidisciplinary team. The latter, MDT, is a group of clinical staff who discuss optimal management of patients with high-risk and more complicated wounds.

Table 3, Anticipated study timeline

Month	Setup	Cohort	Analysis
Nov 2022	Submission to		
	NRES and HRA		
	NIHR portfolio adoption		
Feb 2023	HRA and Trust approval	Start recruitment	
Apr 2024		Finish all recruitment	
Jul 2024		Final visit, last patient	
Aug 2024			Finalise analysis & report

3.2 PRIMARY & SECONDARY OUTCOMES

Outcomes used for all analyses:

- Swab results from the WOUNDCHEK™ Limited kit, with specimen taken at dressing removal, prior to deep wound cleansing.
- Clinical staff member's assessment of infection, with opinion given prior to result of the WOUNDCHEK™ result being known.

4 PARTICIPANTS

4.1 TRIAL PARTICIPANTS & LOCATIONS

Patients with chronic leg or foot ulcers will be recruited into the study. Patients will be recruited from the adult population seen routinely by the evaluation clinical staff.

Identification of potentially eligible patients will be identified by the clinical staff - who themselves form part of the research. Therefore, the patient – carer of / responsible person for the patient - is approached initially by the clinical team caring for them. Only once the patient has given verbal consent to be approached for the study can another member of the study team conduct the consent process and study activities. The clinical staff can also opt to do these activities themselves.

The study will take place in the podiatry, vascular and tissue viability clinics of North Cumbria Integrated Care NHS.

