4.2 INCLUSION & EXCLUSION CRITERIA

Inclusion criteria:

- Adult patients aged ≥ 18 years
- Patients can be newly presenting to or existing users of the specialist service in question (eg podiatry, vascular surgery)
- Patients with recurrent wounds, including multiple wounds, are eligible; largest ulcer to be index wound
- If infection occurs and antibiotics applied, whilst in study, then this is not deemed an exclusion criterion.
- Prophylactic systemic antibiotic use is not an exclusion criterion
- Chronicity: clinical diagnosis of ulcer with wound duration > 30 days.
- Wound type:
 - Leg ulcer (can be venous, mixed or arterial in nature)
 - o Foot ulcer (can be diabetic or non-diabetic in nature)

Exclusion criteria:

- Aged < 18 years
- Any reasons for the patient being unable to follow the protocol, including lack of mental capacity to consent to taking part in the study.
- The patient has concurrent (medical) conditions that in the opinion of the investigator may compromise patient safety or study objectives
- Confirmed and ongoing wound infection at baseline which is already being treated with systemic antibiotics.
- Previous participation in BIOME study

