5.2 STUDY PROCEDURES

Initial assessments at visit 1 (week 0)

After completing informed consent, the nature of the patient's wound will be recorded as well as the other relevant clinical parameters and demographics. The first WOUNDCHEK™ test will also be conducted. See Table 3 for an overview. Dressing selection, dressing frequency and all other aspects of their wound care will continue to be the responsibility of the clinical team – however, if they are influenced in this decision by the result of the WOUNDCHEK™ test then they are asked to record this in the clinical report form.

All visit assessments

Study visits will coincide with standard clinic attendance by patients. At the study visits week0 and week6, a diagnostic swab using the WOUNDCHEK™ infection detection test kit is performed in accordance with the SOP in Appendix 5.

The clinical staff treating the patient will ascertain their opinion regarding infection status of the wound prior to completing the WOUNDCHEK™ detection test, and will therefore be blinded to at least the first result of using the kit. Where possible, a member of the research team plus the clinical assessor will assess result of the WOUNDCHEK™ test.

Table 4, Overview of study activities per time point for different study participants.

Weeks	Visit 1 (wk 0)	Visit 2 (wk 6)#	Visit 3 (wk 12)#
Treatment deviation question	X	Χ	
WOUNDCHEK™ test (method, see appendix 6)	Χ	Χ	
Wound healed status~	n/a	X (if healed, no other	X (if healed, no other
		outcome measures)	outcome measures)
Clinical opinion of ulcer re. infection	Χ	Χ	Χ
PUSH score ulcer size (appendix 3)	X	Χ	Χ
VAS pain scale (appendix 3)	Χ	Χ	Χ
SINBAD score (foot ulcers only, appendix 4)	X	Χ	X
QoL EQ-5D-5L (appendix 5)	Χ	Χ	Χ
Wound measurement*(if standard care	X	Χ	Х
activity)			

[~]Wound status (healed vs non-healed), definition is: complete epithelial cover in the absence of a scab (eschar) with no dressing required bar any protective dressing. There is no minimum length of time that the index site has to have been in said condition for when participant present for follow-up study visit. # Can be \pm two weeks.

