8.1 GENERAL AND BASELINE CHARACTERISTICS

The numbers of patients entering the study will be recorded. Reasons for treatment and study discontinuation, withdrawal and loss to follow-up will be recorded. The date the first patient recruited and last patient completed or termination will also be noted. Protocol deviations including failure to meet inclusion and exclusion criteria will be recorded. Adverse events will also be recorded.

Serious protocol deviations defined as breach of the conditions and principles of ICH GCP or the study protocol, which is likely to effect to a significant degree the safety or physical or mental integrity of the subjects of the study, or the scientific value of the study will be recorded. Patients not withdrawn with a serious device related adverse event will be recorded as a serious protocol deviation.

In order to describe the sample and facilitate analysis of secondary objectives, the following baseline characteristics and parameters will be collated, either from the CRF or the patients' records (using EMIS patient clinical record system), see also Appendix 2:

- Patient demographics, including age and sex.
- Pre-existing co-morbidities, including peripheral arterial disease, diabetes, heart failure.
- Age of and size of foot/leg ulcer wound at baseline
- Dressing used before presentation at baseline.
- Presence or absence of infection

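### The clinical staff whose opinion is compared with the kit also identify the patients, with no consecutive-approach rule or log of those not approached in the text shown

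*Protocol*

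**What the plan says.** On who selects, protocol section 4.1 states: "Identification of potentially eligible patients will be identified by the clinical staff - who themselves form part of the research". The clinical team makes the first approach. Another study team member may then take consent and run the study activities, but "The clinical staff can also opt to do these activities themselves". The sampling frame is broad: "Patients will be recruited from the adult population seen routinely by the evaluation clinical staff". Section 4.2 adds that "Patients can be newly presenting to or existing users of the specialist service in question", so week 0 need not be a first presentation.

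On who rates, section 5.2 states: "The clinical staff treating the patient will ascertain their opinion regarding infection status of the wound prior to completing the" kit test. The treating staff are thus one of the two raters.

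On which attendance counts, section 5.2 says "Study visits will coincide with standard clinic attendance by patients", and the footnote to Table 4 allows weeks 6 and 12 to move by two weeks either way.

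On accounting, section 8.1 says "The numbers of patients entering the study will be recorded", together with discontinuations, withdrawals, losses to follow-up and protocol deviations. It does not mention eligible patients who were not approached or who declined.

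**The concern.** The primary objective in the protocol summary is a difference between two positive rates on the same wounds: clinical opinion and kit. If the chance of entering the study rises or falls with clinical suspicion, the sample is selected on something close to one of the two ratings. That shifts the clinician rate directly. It shifts the kit rate only so far as the two ratings agree. A difference could then be created, enlarged or hidden by who was entered.

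The stated safeguards act elsewhere. Giving the opinion before the kit result protects the rating, not the sampling. Making the largest ulcer the index wound fixes the wound within a patient, not which patient is approached. Without a record of those not approached, a reader of the results could not tell whether selection had occurred, and no later analysis could recover it.

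**Working it through.** **The plan's own figure.** Section 8.2 sets 5% against 9%, a 4-point difference, with a two-sided chi-squared test at 5% significance and 80% power. The effect size is w = sqrt(0.04²/0.95 + 0.04²/0.05) = sqrt(0.00168 + 0.03200) = 0.1835, printed as 0.184. With one degree of freedom this gives N = 234 (power 80.2%), and 234 × 1.10 = 257.4, rounded up to 258. Both stated sample sizes are reproduced. The 4-point target is the yardstick below.

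**Inputs.**
- Starting rate p = 5% for both raters, so the true difference is zero. Section 8.2 gives about 5% for clinical staff; setting the kit equal to it is my assumption.
- Tilt s: how many times as likely a clinician-positive wound is to be entered as a clinician-negative one. The protocol gives no such figure, so a range is shown.
- Overlap a: the share of clinician-positive wounds that are also kit-positive. This is also an assumption. Full overlap is a = 1, and unrelated ratings give a = 0.05. The middle value of 0.40 is illustrative.

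**Formulas.** With Z = s·p + 1 − p:
- Clinician rate after selection = s·p/Z.
- Clinician-positive, kit-negative share = s·p(1 − a)/Z. Kit-positive, clinician-negative share = p(1 − a)/Z.
- Apparent difference, clinician minus kit = p(1 − a)(s − 1)/Z.

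**Tilt of 2.** Z = 0.10 + 0.95 = 1.05. Clinician rate = 0.10/1.05 = 9.5%.
- Full overlap: the kit rate is also 9.5%, so the difference is 0.
- 40% overlap: kit rate = (0.04 + 0.03)/1.05 = 6.7%; difference = 0.03/1.05 = 2.9 points.
- Unrelated: kit rate = 0.0525/1.05 = 5.0%; difference = 0.0475/1.05 = 4.5 points.

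**Other tilts, and tilt at week 0 only.** The 258 samples come from two visits per patient, and selection at entry acts directly only on the first. If equal numbers come from each visit and nothing carries over to week 6, the pooled difference is half the value above.

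| Tilt s | Clinician rate | Difference, all samples (full / 40% / unrelated) | Difference, week 0 only |
|---|---|---|---|
| 2 | 9.5% | 0 / 2.9 / 4.5 | 0 / 1.4 / 2.3 |
| 1.5 | 7.3% | 0 / 1.5 / 2.3 | 0 / 0.7 / 1.2 |
| 1.25 | 6.2% | 0 / 0.7 / 1.2 | 0 / 0.4 / 0.6 |
| 0.5 | 2.6% | 0 / −1.5 / −2.4 | 0 / −0.8 / −1.2 |

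**Starting rates.** The zero at full overlap belongs to equal starting rates. With a tilt of 2 on all samples, starting from clinician 5% and kit 9%, the difference shifts by 0.2 points at the greatest possible overlap and 4.5 if unrelated. Starting from clinician 9% and kit 5%, the order of words in the summary, it shifts by 3.3 and 7.5 points.

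**The case against.** The strongest reply is that this is a possibility, not a demonstrated bias. No document gives a tilt or its direction, and the results depend almost wholly on the tilt and overlap assumed. That stands, and it is why the figures are an illustration with a range that includes zero.

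A reader might set the move from 5% to 9.5% against the 4-point target and infer that selection alone could produce the whole target difference. The documents do not support that as a general statement. The target is a difference between two ratings of the same wound, and the kit rate moves as well wherever the raters agree. Only unrelated ratings, a two-fold tilt and selection acting on all samples together give 4.5 points from equal 5% rates.

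A reader might also infer that staff pick patients with the wound in view, or choose which follow-up attendance is swabbed. The protocol says neither. Section 5.2 records the nature of the wound after consent, and its visit window is an ordinary tolerance. Choice of visit is an inference from the absence of a rule.

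Section 4.2 excludes confirmed infection already treated with systemic antibiotics at baseline, which limits over-entry of the most obvious cases. Untreated and possible infections remain open to selection.

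Finally, a screening step could appear in the Appendix 2 flowchart, which is not shown, so the absence can be stated only for the visible text.

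**Conclusion.** The point holds as a weakness in the sampling method. One of the two raters identifies and first approaches the patients, existing service users can enter at any attendance, and the visible text has neither a consecutive-approach rule nor a record of those passed over. From equal 5% rates and an assumed two-fold tilt, the resulting bias in the primary difference lies between 0 and 4.5 points, or about 0 to 2.3 if only week-0 samples are affected. A tilt of 1.25 to 1.5 moves the clinician rate by 1.2 to 2.3 points. Under-entry of suspicious wounds would act in the opposite direction. The documents establish neither the direction nor the size of any actual tilt. The case for change is that the remedy is cheap and must be in place before recruitment.

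**What to change.** In section 4.1, require that all eligible attenders at participating clinic sessions are approached consecutively from the clinic list. Keep a log of those not approached or declining, with wound type and reason, and report it with the results. If the Appendix 2 flowchart already contains such a step, state it in 4.1 as well.

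As a minor addition in section 5.2, define the week-6 study visit as the routine attendance nearest day 42 within the existing window. This is a precaution, since the protocol does not say that staff choose the visit.

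The cost is a log built from existing clinic lists, a few sentences of protocol text and some clerical work by clinic staff. The sample size does not change.
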